# Data collection

Following triage, intervention pharmacies will collect the following data:

# a. Usage and referral data

The rationale for this intervention is to lower access barriers. The primary area of interest is therefore the number of consultations, severity of danger and number of referrals made as a consequence of the consultation. Other measures we will explore include the reasons why the client chose the service, whether the client was considering or had accessed other services in the last 3 months,

The member of staff conducting the consultation will record the date, time, length of consultation, job role of staff member and the category of issue. Following triage, the informed consent will be received from the client. Data to be collected will include asking the client what services he/she has accessed in the last 3 months, and whether he/she has accessed this service previously. The client will then be asked some simple questions about reasons for choosing this service based on the four access barriers (capacity, psychological burden, timing and level of severity), for example: no appointment needed, convenient location, everyday environment, identified with the name and logo, convenient timing, familiar environment, familiar staff, whether their visit was opportunistic or planned, and basic demographic data.

Brief acceptability data will also be collected along with basic demographic details plus an indication of whether (for a future trial) completing a questionnaire and having a follow-up contact would be acceptable or not.

Staff will be trained to respond ethically in all cases of acute and severe distress by prioritising the safety and wellbeing of the client over the need to consent and collect data for the study. In some cases, this may mean that it may not be appropriate under very distressing circumstances to collect all of the client's study data.

#### b. Business data

Business data will be collected in order to evaluate whether taking on the service detracts or enhances normal pharmacy activity. Data will include prescription and service items. These data will be collected at the beginning of the study retrospectively for the 6 months prior, and during the 6 months of the implementation. All costs of the intervention will also be recorded.

In the control (comparison) pharmacies, the same business data will be collected in addition to the number of queries or interventions made for domestic abuse, and for suicidal ideation, and whether any of these were through an alternative scheme (for example "Ask for ANI"). We are including control pharmacies as this will provide useful data for a future trial and because we anticipate that the baseline levels of requests for assistance with DA will increase with public awareness of "Ask for ANI".

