Outcome Measures	The primary outcome measure for this study will be the number of community pharmacy consultations for people enquiring about or seeking support for domestic violence or suicidal ideation. Secondary outcome measures are (i) to determine the levels of severity
	of danger that clients present and (ii) subsequent management and

Page 7 of 50

	successful referrals to support organisations (iii) Cost and economic considerations.
Data Analysis	Following transcription of the qualitative data, analysis will proceed through an initial iterative process of open coding and according to the consolidated coding framework. After the coding process has been completed, a more refined and selective process of 'coding on' will be undertaken to differentiate, contrast and narrate the emerging themes that are of relevance to meeting the study's objectives. The qualitative software programme NVIVO 11 will be used to organise the data. The quantitative data analysis will use descriptive comparison between intervention and control pharmacies, and appropriate multivariable linear regression. Data will be analysed using R Version 3.

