#### STUDY MANAGEMENT COMMITTEES

Lincoln Clinical Trials Unit (LinCTU). The co-investigator GL is deputy-director of the CTU. The CTU's involvement will consist of setting up all of the progression criteria and associated data collection on CASTOR trials software. The CASTOR software will allow data recording templates to be available to the pharmacies online so that they can enter the data at the time of the consultation, and the data will go directly to the database. It also allows the research team to have access to live and comprehensive data. The CTU will ensure full GDPR compliance and that all data is stored in secure cloud access in the UK. They will assist with participant information sheets, consent forms and applying for ethical approval. The CTU will also conduct all randomisation and statistical analysis, and provide data monitoring and study support. GL and the LinCTU will play a significant role in the final evaluation of feasibility.

**Study Steering Group**. The Study Steering Group will meet every six months to ensure all practical details of the study are progressing well and to ensure adherence to timescales and reporting to NIHR.

**Patient and Public Involvement and Engagement (PPIE) Panel**. The PPIE panel will meet bi-monthly to ensure the study remains sensitive to patient and public preferences at all stages. Specifically, they will be involved in reviewing all study participant and public facing materials, co-developing the response service and evaluation of the main findings.

**Study Management Group**. The Study Management Group consists of the research team, co-investigators and relevant local partners. They will meet bi-monthly to discuss the progress of the study and discuss the findings as they emerge.

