### **OUTCOME MEASURES/ENDPOINTS**

#### PRIMARY OUTCOME MEASURE/ENDPOINT

The primary outcome measure for this study will be the number of community pharmacy consultations for people enquiring about or seeking support for domestic violence or suicidal ideation, categorised per issue and level of severity.

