#### Quantitative data

There are three sets of quantitative data: the evaluation of pharmacy staff learning, the intervention measures and the community e-survey. To assess the impact on pharmacy staff learning (using the CPD Reaction Questionnaire), baseline and post-training data scores will be compared. For both the CPD Reaction Questionnaire and the community e-survey, categorical variables will be analysed using the chi-squared test or Fisher's exact test as appropriate. Continuous data will be analysed using the within-group t-test or Wilcoxon signed rank-test as appropriate. Statistical significance will be assessed at the 5% (two-sided) level. All statistical analyses will be conducted using IBM Statistical Package for Social Sciences (SPSS) 22.

All client and pharmacy intervention / control data will be processed using R Version 3. The demographics and characteristics of the samples will be initially summarised using frequencies and percentages for categorical variables and mean and standard deviation (if normally distributed) or median and interquartile range (if not normally distributed) for continuous variables.

The main outcome in this feasibility study is the number of community pharmacy consultations for people enquiring about or seeking support for domestic violence or suicidal ideation per issue and level of severity. Descriptive comparisons will be made between intervention and control pharmacies. Appropriate multivariable linear regression models will explore differences between intervention and control groups in means and 95% CIs. As the feasibility study is not powered to detect effectiveness, the focus will be on whether 95 % CIs include a meaningful difference. This will seek to inform a sample size calculation for a future definitive trial.

The final evaluation of feasibility will involve the integration of the qualitative and quantitative data and will include an economic evaluation. In the economic analysis, a societal perspective will be taken into consideration. Business data including staff time will be used to inform the findings. Cost per client will be estimated by dividing the costs of the response service by the total number of clients accessing the service in the intervention group. An incremental cost-effectiveness ratio (ICER) will be determined to explore the affordability and potential cost-effectiveness of the intervention and inform a future trail rather than provide a definitive comparison

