24	Client basic demographic data collected in consultation	Data sheets in pharmacies	Staff able to complete at least 80% of the data for at least 80% of the clients	Failure to record at least 50% of the data for at least 50% of the clients	Failure to record at least 30% of the data for at least 30% of the clients	
25	Willingness to be followed up	Data sheets in pharmacies	Staff able to complete at least 80% of the data for at least 80% of the clients	Failure to record at least 50% of the data for at least 50% of the clients	Failure to record at least 30% of the data for at least 30% of the clients	
26	Pharmacy business data - prescription and service items. These data will be collected at the beginning of the study retrospectively for the 6 months prior, and during the 6 months of the implementation (for both control and intervention)	Pharmacy companies	Able to collect at least 90% of the data from 90% of the intervention pharmacies		Failure to collect at least 50% of the data from 50% of the intervention pharmacies, or an indication from this data that the intervention is having a deleterious effect on the business and staff wellbeing in any one of the pharmacies.	
27	Control pharmacies – number of queries for SI or DA, and if any Ask for ANI / safe space requests	Pharmacy companies	Able to collect at least 80% of the data from all 4 intervention pharmacies		Failure to collect 50% of the data from any one of the intervention pharmacies	
28	Community survey responses	Community survey	Completion of 600 full responses to community survey within the time period	Completion of 400 full responses to community survey within the time period	Completion of 300 or less full responses to community survey within the time period	
29	Acceptability and effectiveness of training using the Theoretical Framework for Acceptability of Healthcare Interventions – in staff focus groups	Staff focus Groups	All staff reporting that the training and ongoing support had sufficiently prepared them for completed the undertaking the intervention	Four or more staff reporting that the training and ongoing support had not sufficiently prepared them for completed the undertaking the intervention	Half or more of all staff (12/24) reporting that the training and ongoing support had not sufficiently prepared them for completed the undertaking the intervention	

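### Controls record no severity, so the main outcome cannot be compared by severity; its total and per-issue counts are collected differently in the two arms and cannot be separated from recording

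*Protocol*

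**What the plan says.** **Outcome.** The section Primary outcome measure/endpoint counts consultations "categorised per issue and level of severity". Data analysis, Quantitative data, repeats this as the main outcome and goes straight on to the between-arm comparison: "per issue and level of severity. Descriptive comparisons will be made between intervention and control pharmacies". It adds a model: "Appropriate multivariable linear regression models will explore differences between intervention and control groups in means and 95% CIs". The result is meant to inform the sample size of a definitive trial. The Study summary places severity elsewhere: "Secondary outcome measures are (i) to determine the levels of severity".

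**Intervention pharmacies.** At least three staff per pharmacy are recruited and trained. They take each client through triage questions that assign a level on the grid. The section Study management committees makes online templates available to pharmacies "so that they can enter the data at the time of the consultation". Appendix 1, criterion 20, takes issue and severity from the triage grid.

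**Control pharmacies.** Phase 2, part E, b. Business data, collects the same business data "in addition to the number of queries or interventions made for domestic abuse, and for suicidal ideation", plus whether any contact came through another scheme such as Ask for ANI. The Schedule of procedures lists enquiries and referrals instead. Appendix 1, criterion 27, has "number of queries for SI or DA, and if any Ask for ANI / safe space requests", with pharmacy companies as the source.

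**The concern.** A comparison needs the same quantity measured in the same way in both arms. Here one dimension of the main outcome exists in one arm only, and the count itself differs by arm in its unit, its recorder and its source. Staff are not blinded.

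The study is declared not powered for effectiveness, so a false efficacy claim is not the main risk. The risk lies in what is carried forward. The protocol wants to read the 95% confidence interval for a meaningful difference, and Appendix 1, criterion 35, asks for the feasible between-group difference and the intraclass correlation. If recording differs by arm, both come from counts that are not comparable. An overstated difference makes the next trial too small; an understated one makes it too large or looks like a reason not to run it.

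Ask for ANI adds to this. The protocol includes controls partly because it expects that scheme to raise baseline requests. Such contacts are explicitly flagged only in controls, so they cannot be set apart in the same way in both arms.

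**Working it through.** **1. No plan figure to reproduce.** The protocol gives no contact rate, capture rate, effect size or power for this outcome. The allocation arithmetic agrees: 4 categories × 2 = 8 intervention pharmacies, 4 × 1 = 4 controls, 12 in all.

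**2. The two arms side by side.**

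| Element | Intervention (8) | Control (4) |
|---|---|---|
| Unit | Triaged consultation | Queries or interventions (Business data); enquiries and referrals (Schedule); queries (criterion 27) |
| Recorder | Staff recruited and trained for the study | None recruited or trained |
| Route | Online templates or data sheets, at the consultation | Pharmacy companies (criterion 27); no consultation form specified |
| Issue | Recorded | Recorded, domestic abuse and suicidal ideation separately |
| Severity | From the triage grid (criterion 20) | No item in any of the three places |
| Other scheme, e.g. Ask for ANI | Not explicitly listed | Flagged |

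**3. Severity.** The draft grid has three levels. With 2 issues this gives 2 × 3 = 6 cells, and none has a control value. No analysis plan can recover data that were not collected.

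**4. Totals and per-issue counts.** Let c_I and c_C be the shares of true contacts that reach the count in each arm. Then

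observed ratio = true ratio × c_I / c_C.

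With a true ratio of 1 and assumed capture:

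| c_C | c_I = 1.0 | c_I = 0.8 |
|---|---|---|
| 0.9 | 1.11 | 0.89 |
| 0.7 | 1.43 | 1.14 |
| 0.5 | 2.00 | 1.60 |
| 0.3 | 3.33 | 2.67 |

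The ratio can fall on either side of 1.

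**5. What this could do to the planned interval.** A linear model with arm and three category indicators on 12 pharmacies leaves 12 − 5 = 7 residual degrees of freedom. It was simulated 20,000 times per setting with Poisson counts, no true effect and full capture in the intervention arm. The share of runs in which the 95% interval excludes zero was:

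| Assumed mean contacts per pharmacy | c_C = 1.0 | 0.7 | 0.5 | 0.3 |
|---|---|---|---|---|
| 5 | 5% | 15% | 39% | 73% |
| 10 | 5% | 28% | 70% | 96% |
| 20 | 5% | 51% | 94% | 100% |

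At a mean of 10 the apparent difference is 3.0, 5.0 and 7.0 contacts at control capture of 0.7, 0.5 and 0.3. Means and capture shares are all assumed. Variation between pharmacies beyond Poisson would lower the shares above 5%. With equal capture the problem disappears.

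**The case against.** The strongest case on the other side has four parts.

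- **Controls are engaged.** They consent as sites, receive £500, are asked for this very count, and criterion 27 makes obtaining it a progression criterion. The online templates are offered to pharmacies without excluding controls.
- **Forms are not final.** The Modelling step leaves data collection documents and feasibility outcomes to be finalised before Phase 2.
- **Stakes are limited.** This is a feasibility study, and whether controls can supply counts is part of what it tests.
- **Missing control severity follows from usual care.** Controls have no triage tool, and per-issue comparison remains possible.

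Much of this stands, and it rules out two stronger readings. A reader might infer that control staff will under-record and so inflate the effect. The documents give no capture figure, and intervention recording may also be incomplete: staff may omit study data when a client is in severe distress, and are trained to invite clients at Levels 1 and 2. A reader might also infer that the intervention count is restricted to consenting adults while the control count is not. The text is mixed. The eligibility criteria require age and consent, but the usage data section has staff record date, time and issue before it mentions consent, and service may be delivered on Part A data alone.

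The objection does not remove the core. The Modelling step promises no shared definition or log, and the protocol still fixes a comparison by severity for which controls collect nothing.

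**Conclusion.** The point holds in two parts of different certainty.

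- **Severity.** The between-arm comparison of the main outcome by severity cannot be made: all six issue-by-severity cells lack control data. This needs no assumption beyond the protocol's own data lists. The Study summary also disagrees with the outcome and analysis sections on whether severity belongs to the primary or a secondary outcome.
- **Totals and per-issue counts.** These can be compared, but the difference mixes any effect of the service with differences in unit and recording. A real effect would also show, so the comparison is confounded rather than empty. The documents fix neither the size nor the direction of the distortion; the ratios of 2 and 0.89 are illustrations under assumed capture.

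As written, the plan passes this difference, and the intraclass correlation, to the design of the next trial. It should be corrected.

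**What to change.** 1. Define the between-arm outcome as the number of domestic abuse and suicidal ideation contacts per pharmacy, in total and per issue, with one written definition of a contact.
2. Use one minimal anonymous log in all 12 pharmacies: date, issue, and route (this service, Ask for ANI, other). Send the same reminder to both arms.
3. Report severity descriptively in the intervention arm only.
4. Align the Study summary (Outcome Measures), Primary outcome measure/endpoint, Quantitative data, b. Business data, the Schedule of procedures and Appendix 1, criterion 27. The thresholds of criterion 27 also need correcting: the criterion is about controls, but they refer to four intervention pharmacies, and there are eight of those.

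**Cost.** Amendment wording, log access and brief instruction for staff in four control pharmacies, and a regular reminder. The log may raise control staff's attention to these contacts and so somewhat reduce the contrast between arms. That is a fair price for a count that means the same thing in both.

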# F. Evaluation for acceptability

# 1. Post-intervention pharmacy staff focus groups

In-depth qualitative focus groups will be held with all staff that participated in the intervention (x3 with 8 participants in each). A topic guide will be devised to cover perceptions of the acceptability and effectiveness of the training and the entire intervention, using the Theoretical Framework for Acceptability of Healthcare Interventions.

#### 2. One-to-one pharmacy customer interviews

Similarly, in-depth qualitative interviews will be held with 2-3 regular customers (using purposive sampling for demographics) from each of the eight participating pharmacies (16-24 in total). Customers will be recruited through the pharmacy by approaches from the pharmacy staff with a flyer and expression of interest response box / e-mail. These will be general customers rather than clients who have used the service, with the aim of ascertaining community perceptions towards the use of a pharmacy for this service and impact of the response service on other services. Customers will receive a £15 gift voucher as an appreciation of their participation. Interviews will be offered in English, Polish, Lithuanian, Hindi and Urdu.

Both the focus groups and interviews will be audio recorded and then transcribed verbatim. All identifiable information will be removed during the transcription. Participants will be given a study code as an identifier. The data will then be analysed using framework analysis, and the qualitative software programme NVivo 11 will be used to facilitate organisation of the data.

#### 3. Public e-survey

The themes from the combined qualitative analysis will be used to form the basis of a quantitative e-survey. The rationale of the community survey is to measure the wider awareness of the service.

The e-survey will be distributed through local community networks (the same as were used in the promotional strategy), and the intervention pharmacies, and will evaluate public awareness and attitudes towards acceptability and accessibility. The survey will contain a participant information section. A total of 600 responses will be aimed for. Assuming a response rate of 50%, 1200 people will need to be specifically targeted. Students will be employed through the University of Lincoln's "Campus Jobs" scheme to conduct market research by approaching passers-by in community settings and promoting on social media. Data from the survey will be analysed using descriptive and comparative statistics for different demographic groups.

**G. Feasibility of the intervention -** A summary workshop will be held with the 24 staff members, plus PPIE panel and Study Management Group will be held to explore the feasibility of the intervention as a possible

service and to review and finalise the intervention. Consideration will be given to: any unintended or adverse consequences, the degree of local adaptation that would be required, who would deliver the training, who would deliver the mentoring, factors that facilitate/hinder the intervention, and its overall benefits and limitations of the intervention. This would enable us to fully describe the intervention, and its components, plus the extent to which it can be adapted, so that it can be reproduced faithfully. The topic guide for the workshop will be based on the Consolidated Framework for Implementation Research. Pharmacy staff participants will receive a £75 for participating as a token of appreciation (or a voucher if preferred), as this will be an additional event after the 6 months implementation, for which the pharmacy received a fee.

The workshop will use breakout rooms to work in small groups, with audio recording of each group, and then a plenary as one large group, which will also be audio recorded. The recordings will be transcribed verbatim. Analysis will proceed through an initial process of open coding and according to the consolidated coding framework. After the coding process has been completed, a more refined and selective process of 'coding on' will be undertaken to differentiate, contrast and narrate the emerging themes that are of greatest relevance to the study's objectives.

This process will be used to refine and describe the entire intervention, each individual intervention component, the acceptability (for both provider and service user), intervention fidelity and delivery of the intervention and the process of implementation.

If the intervention is found to be cost-effective in a future trial, it is envisioned that the service could be adopted under the national pharmacy contract as an advanced service, in a similar way to the Medicines Use Review (MUR) / New Medicines Service (NMS), which requires pharmacists to be trained and accredited by a Higher Education provider. JS has experience in this area, having led the provision of MUR accredited training to a major multiple pharmacy and AL's PhD was on the MUR service and postdoctoral work on NMS. If adopted nationally, regional triage and referral resources would need to be developed to ensure effective local implementation.

